4. Cost and consequences of PCIT versus CPP using a cost-consequence analysis as they relate to treatment effect size (improvement from baseline), clinical costs, and perceived social validity. CPP is hypothesized to yield comparable effects but at less cost and with greater satisfaction.
5. Degree to which parent stress and depressive symptoms moderate intervention effectiveness for PCIT and CPP. It is hypothesized that there will be no difference between PCIT and CPP in the moderating effects of baseline parent stress and depressive symptoms on parent or child behavior.

In addition, **one exploratory aim will be tested:** Is PCIT more effective than CPP for some families? It is possible that PCIT is more effective for families with specific risk factors. We will examine differences in PT program effects based on baseline child behavior problems (severity of behavior problems; externalizing versus internalizing problems) and degree of family social risk.

3. Background:

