Exclusion criteria are parent(s) who (a) has (have) severe mental illness that would interfere with their ability to participate in PT (measured by the Psychosis Subscale of the Basic-24 or diagnostic intake clinician assessment) and/or (b) is (are) actively using drugs or alcohol, based on clinician assessment at intake. Foster parents or relatives without legal status for the child are excluded since they may not be able to complete the study.. Children who are actively suicidal, psychotic, or who have significant developmental delay (i.e., fail developmental screening using Ages and Stages Questionnaire at intake), congenital, genetic, or sensory abnormalities that interfere with the child’s understanding, cooperation, and/or participation in PCIT or CPP will be excluded and referred for appropriate treatment services or hospitalization. Children diagnosed with autism or Pervasive Developmental Disorder will also be excluded since there is no evidence that CPP or PCIT is effective with these populations.

6. Drugs/ Substances/ Devices

- a. NA
- b. NA.
- c. NA

7. Study Statistics

- a. Primary outcome variables: Child behavior problems (parent report and observed from video recorded parent-child play/clean-up), parenting self-efficacy, parent discipline, parent behavior (observed from video recorded play/clean-up), parent satisfaction, parent engagement in the intervention, parent attendance in PT sessions.
- b. Secondary outcome variables: cost variables are those related to (1) time required to administer PT (including lost time for missed appointments) and additional non-PT therapy services used by parent or child (i.e., individual therapy, medications); (2) therapist time, (3) parent time, (4) childcare provided during CPP sessions; (5) space (including one-way mirror).
- c. Sample Size and Statistical Plan: Sample size in this equivalence study is designed to determine whether CPP is as effective as PCIT for the targeted clinical population (i.e., outcomes do not differ clinically or statistically). We used CBCL scores (child behavior problems) to estimate the sample size positing the null hypothesis that the absolute difference in the post intervention means between the CPP and PCIT groups will be > 0.5 standard deviations (i.e., > 5 point difference on the CBCL). The alternative hypothesis is that the absolute difference in the two means is less than or equal to 0.5

Date: January 30, 2012
Principal Investigator: [name]

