- c. Plan for reporting unanticipated problems/study deviations. A Data, Safety, and Monitoring Plan will be comprised of 6 members who will monitor (a) the conduct of the study, (b) recruitment/retention rates, (c) participant satisfaction, (d) the safety of participants, and (e) the validity and integrity of the data. The committee will include the PI ([name]) and the Co-PI ([name]) and four additional members who are not members of the research team: an experienced child psychiatrist, a biostatistician, a clinical trial expert, and a community member. If an adverse event occurs, the event will be reported within 48 hours to the Johns Hopkins University School of Medicine IRB and the NIH Project Officer using the JHU IRB Protocol Event Report with supporting documentation.
- d. Confidentiality: The parent/child participants are all patients of the Family Center and will be provided with the same confidentiality afforded to all patients receiving care at the Family Center at Kennedy Krieger Institute. We will also apply for a Certificate of Confidentiality. Clinicians will not be required to provide personal information as a part of this study.
- e. Financial risks to the participants: Parent training is considered routine care and will be billed to the child's insurance. Childcare will be paid by a grant. There is no financial risk associated with parents' participation in this study.

9. Benefits

Date: January 30, 2012
Principal Investigator: [name]
Application Number: NA_00039328

All participants will receive treatment and both PT treatments offered in this study have been shown to be effective for improving parenting behavior and reducing behavior problems in young children. The potential benefits include: (1) improved child behavior, (2) parent use of more positive child management strategies, (3) improved quality of parent-child relationships, and (4) increased parenting self-efficacy. Since parents in the study will be able to access additional treatments as needed, it can be expected that parents and children who participate in this study will experience improved mental health and wellbeing. Therapists will receive confidential support and supervision for their work with the families.

10. Payment and Remuneration.

Parents who participate in this study will receive the following:

- \$30 gift cards for each fully completed set of assessments (\$90 total for all 3 assessment phases)

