- A book for the target child after each completed assessment phase (value approximately \$5)
- If participants complete all 3 assessment phases, they will also receive a free copy of their video-recorded parent-child play sessions (collected as part of the assessment battery)
- Free childcare at the Family Center for children not involved in the study treatment sessions during the time their parent is attending the study treatment.
- If parent groups are scheduled during the dinner hour (between 5:30 and 8pm), parents and children in the CPP condition will receive free dinner during the study treatment sessions
- Taxi vouchers for participants to and from study treatment sessions

11. Costs

There are no costs associated with participation in this study.

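### Sibling childcare is costed in CPP but not in PCIT, although both arms are offered it, which tilts the childcare part of the Objective 4 cost comparison against CPP

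*Combined protocol and SAP*

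**What the plan says.** Section 2, Objective 4, sets up a cost-consequence analysis and states its expectation: "CPP is hypothesized to yield comparable effects but at less cost and with greater satisfaction". The cost variables are secondary outcomes in section 7, item b. They cover the time to deliver parent training and non-PT services, therapist time, parent time, and then "4) childcare provided during CPP sessions; (5) space (including one-way mirror". This is the only childcare item. Meals and transport do not appear.

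Section 10 opens its list with "Parents who participate in this study will receive the following" and names no arm. One entry reads "Free childcare at the Family Center for children not involved in the study treatment sessions during the time their parent is attending the study treatment". Another is "Taxi vouchers for participants to and from study treatment sessions". The dinner entry is the only one limited to an arm: when groups meet in the dinner hour, "parents and children in the CPP condition will receive free dinner during the study treatment sessions".

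Section 4, item b, explains that childcare accompanies CPP because the target child does not attend the groups. In PCIT the target child is in the session. Section 8, item e, says that a grant pays for childcare. The Abstract says that clinical costs are measured monthly. No section states a costing perspective.

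**The concern.** The same service, care of children other than the target child while the parent is in treatment, is offered in both arms but would enter the cost total in only one. Below, sibling care means care of any child other than the target child.

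Item (4) is worded by session type, not by child. It therefore takes in all childcare at CPP sessions, siblings included, and none at PCIT sessions. Cost is half of the argument for CPP (comparable effects at lower cost), and an accounting rule that differs by arm goes straight into that difference. If sibling hours by family are not logged during the trial, they may be hard to rebuild afterwards.

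**Working it through.** **What can be reproduced.** The plan gives no cost figure. The one stated number that drives these items is about 24 hours of exposure per arm (section 4, item b).
- CPP: 12 sessions × 2 h = 24 h. This agrees.
- PCIT: 24 h ÷ 1 h per session = 24 sessions. Section 3 gives 10–20 one-hour sessions for most families in published work, and longer courses for low-income families. I use s = 10, 20 and 24 PCIT visits.

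**Childcare alone.** Let c be the cost per child-hour and m the number of siblings in care per family, with full attendance.
- CPP − PCIT as listed: 24(1 + m)c − 0.
- Rule A, all childcare in both arms: 24(1 + m)c − s·m·c. The list overstates CPP − PCIT by s·m·c.
- Rule B, only target-child care, which the CPP format requires: 24c. The list overstates CPP − PCIT by 24·m·c.

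Under either consistent rule the error has the same sign, against CPP, and it is zero only if no siblings use the service. With m = 1, the uncounted PCIT volume under rule A is 10 to 24 hours. At an assumed $5–20 per hour that is 10 × $5 = $50 up to 24 × $20 = $480 per family using it. The rule B excess is 24 × $5 = $120 up to 24 × $20 = $480. Averaged over an arm, these figures shrink with uptake, which the documents do not give.

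**Adding dinners and taxis.** Round trips per fully attending family are 12 in CPP against 10, 20 or 24 in PCIT, a PCIT:CPP ratio of 10/12 = 0.83, 20/12 = 1.67 or 24/12 = 2.0. Further assumptions, none from the documents: taxi t = $10–40 one way; dinner d = $5–20 per head for two people at all 12 CPP sessions (12 × 2 = 24 meals). The amount to add to the listed CPP − PCIT difference, with rule A and m = 1, is

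−s·c + 24d + (24 − 2s)t

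| PCIT visits s | Childcare −s·c | Dinners 24d | Taxis (24 − 2s)t | Net range |
|---|---|---|---|---|
| 10 | −$200 to −$50 | +$120 to +$480 | +$40 to +$160 | −$40 to +$590 |
| 20 | −$400 to −$100 | +$120 to +$480 | −$640 to −$160 | −$920 to +$220 |
| 24 | −$480 to −$120 | +$120 to +$480 | −$960 to −$240 | −$1,320 to +$120 |

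For example, the lower end at 24 visits is −480 + 120 − 960 = −1,320, and the upper end is −120 + 480 − 240 = +120. The net range crosses zero at every visit count. The taxi term itself changes sign at s = 12.

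**The case against.** The strongest reply is that CPP childcare belongs to the delivery model, because the target child is excluded from the group, while sibling care in PCIT is a study convenience. A programme-cost perspective could then properly charge childcare to CPP alone. This explains why CPP childcare should be the larger item. It does not rescue item (4), which is not confined to target children: CPP siblings are counted and PCIT siblings are not.

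A second reply is that dinners and vouchers sit under Payment and Remuneration with gift cards and books, while the plan speaks of clinical costs. That stands. A reader might infer that leaving out meals and taxis is itself an error; the documents do not support this, because excluding study inducements is a legitimate perspective. What remains is that the boundary is unstated. The cost list includes parent time and grant-paid childcare, and childcare is in the same section 10 list.

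Third, cost is a secondary outcome with no threshold or cost-based sample size, and the list names broad categories in a protocol, not a costing manual. This limits the consequence but does not remove the asymmetry.

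Fourth, attendance is recorded after each session (Table 1), and grant-paid childcare can be expected to leave expenditure records. A reader might infer that the comparison would be beyond repair. That goes too far: much may be recoverable, though sibling hours by family may not be.

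**Conclusion.** The point holds for childcare. As written, sibling care is charged to CPP and not to PCIT, which biases the Objective 4 cost comparison against CPP. The size cannot be computed from the documents: it depends on uptake, PCIT visits and unit cost, none of which is fixed. PCIT childcare excludes the target child, so its volume is probably smaller than in CPP.

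A reader might infer that the cost list flatters CPP, or that the whole cost conclusion is off by a known amount. Neither follows. The childcare error runs against the plan's own hypothesis. Once unlisted dinners and taxis are considered, the net direction is unknown. The dollar ranges are illustrations that assume unit prices, full attendance, one sibling in care and dinner at every CPP session. They show that the sign of the correction is not fixed, and they do not estimate its size. This is worth correcting because it is cheap, but it does not touch the effectiveness analyses.

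**What to change.** Reword item (4) of section 7, item b, as *childcare provided during PCIT and CPP sessions*. Record it by actual use per family with the monthly cost data, with target-child and sibling care kept separate. State the costing perspective.

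As a secondary step, record CPP dinners and taxi vouchers (both arms). Report one sensitivity analysis that includes them and one that leaves childcare, meals and taxis out of both arms alike. The base case may omit meals and taxis, provided that the plan says so. The 24 hours given for PCIT in section 4 and the 10–20 one-hour sessions in section 3 should also be reconciled, since the visit count drives these items.

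The cost is a short childcare log, a few entries from study expenditure records, and two extra analyses. The design, sample size and clinical procedures are unchanged.

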CPP groups are led by two trained group leaders using a standardized manual that lists specific discussion questions associated with each video vignette. Typically, 8-12 parents are enrolled in a 12-session CPP group (unlike PCIT, parents are encouraged to bring other family members to the CPP

Date: _ January 30, 2012 _____
Principal Investigator: _ [name] _____
Application Number: _ NA_00039328 _____

sessions for support). The vignettes are designed to stimulate discussion and problem-solving around each of the vignettes and the group leaders help parents tailor strategies to meet their childrearing goals. Although CPP group leaders are experts about the child behavior management strategies and program principles, they are trained to view parents as the experts about their own children. Thus, the parent groups are designed to help parents (a) clarify their childrearing goals and (b) select those strategies they believe will be most effective and most likely to advance their childrearing goals. This aspect of CPP lies in contrast to PCIT, where treatment progress is dependent on parents mastering each skill taught in the program before acquiring a new skill.

The CPP was rigorously evaluated in a randomized trial of 253 parents of 2-4 year old children in 7 childcare centers serving low-income families in Chicago (59% African American, 33% Latino). Parents in the CPP condition used less corporal punishment and had more positive observed interactions with their children at 1-year post-intervention when compared to control parents. In addition, their children exhibited significantly fewer behavior problems during observed parent-child interactions. Parents who attended at least half of the CPP sessions also reported higher parenting self-efficacy, more consistency in their discipline, and fewer behavior problems at home. In addition, teacher-ratings of children's behavior problems in child care showed significant improvements. Parent stress and depression did not moderate these outcomes. Moreover, consumer satisfaction was high; parents reported that they would highly recommend (85%) or recommend (15%) the program to other parents.

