- a. Design: This equivalence study will use an experimental design with randomization of parents seeking behavioral treatment for their 2-5 year old children at the Family Center (FC) in [name]. Equivalence studies are used to determine whether a novel treatment or health delivery model, that might be less costly or more acceptable to the treatment population, is at least as effective as another more well-established treatment. It is important to note that the participants in this study, who experience multiple adversities associated with urban poverty and mental health problems, may require more therapeutic services than just PT. As a result, parents and children may receive additional treatment (e.g., individual therapy, medication) other than PT. However, PT treatment (PCIT or CPP) will be randomly assigned and all additional therapies provided to the participating parent or child at the Family Center or other agencies during the course of this study (type, amount, and cost) will be accounted for in the study and included as co-variates in the analyses. In addition, the effect of parent depression and stress on PT outcomes will be evaluated. The strengths of this design include (a) the ability to determine whether families exposed to one PT program need more additional treatment than families exposed to the other PT program, (b) the ability to estimate the costs of additional therapy, (c)

Date: _ January 30, 2012 _____
 Principal Investigator: _ [name] _____
 Application Number: _ NA_00039328 _____

greater buy-in from clinicians who may be concerned that randomization will negatively affect treatment outcomes for their families, and (d) enhanced external validity of the study.

This study will use a block randomization procedure to facilitate the initiation of parent groups without lengthy waiting periods. Each block will consist of the next 19 eligible parents (estimated recruitment time=3-4 months). Following intake assessment by a FC clinician to determine study eligibility, parents who meet the inclusion criteria will be invited to participate in the study. Parents who state interest in participating and agree to have their name given to the Project Director will meet individually with the Project Director (to be hired) who will describe the study and obtain informed consent. Documentation of parent's agreement to be contacted by the Project Director will be placed in the child's medical record.

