b. Study duration and visits: Following consent, parents will be assigned to the appropriate block consisting of the next CPP group or the next available PCIT therapist. Participating parents and children will complete three assessment phases: baseline, 4 months post-baseline, and 9 months post-baseline. Each assessment phase includes parent-report surveys on child behavior problems, parenting self-efficacy, parent discipline strategies, stress, depressive symptoms, and attachment, and a 15- minute videotaped parent-child free play interaction (Dyadic Parent-Child Interaction Coding Systems; DPICS), followed by a clean-up session. Videotaped DPICS assessments will be coded by research colleagues at the University of Iowa ([name].) A Data Use Agreement will be obtained between Drs. [name], University of Iowa and [name], Johns Hopkins School of Nursing. Assessments typically require 45-75 minutes at each phase. All measures are described in Table 1 below.

Table 1. Parent-Child Variables, Measures, Informant, Items, Assessment Time-points*, Reliability, Validity

Variables	Measure(s)	Informant	# of Items	When Assessed	Reliability	Validity Evidence
Child Behavior Problems (parent)	Child Behavior Checklist (CBCL/1½-5) (Externalizing Scale & Internalizing Scale)	Parent	99	T1, T2, T3	.86-.89	[40; 41]
Child Behavior Problems (observed)	Dyadic Parent-Child Interaction Coding System (DPICS) (non-compliance, destructives, physical negatives, smart talk, cry, whine, yell)	Observer	7	T1, T2, T3	.73	[22; 57; 58]
Parent Self-Efficacy	Toddler Care Questionnaire (TCQ)	Parent	38	T1, T2, T3	>.93	[22; 57; 59; 60]
Parent Discipline	Parenting Questionnaire (PQ) (Warmth, Following Through, Corporal Punishment subscales)	Parent	50	T1, T2, T3	.68-.84	[22; 61]
Parent Depression	Center for Epidemiologic Studies Depression Scale-Revised	Parent	20	T1, T2, T3	>.85	
Parent Attachment	Attachment Style Questionnaire	Parent	40	T1	Test-retest .75-.80	
Parent Behavior	DPICS (Praise, Commands, Physical Coerciveness, Critical Statements, Positive/ Negative Affect)	Observer	10	T1, T2, T3	.88-.90	[22; 57; 58]
Social Validity: parent satisfaction w/ PT	Parent Satisfaction at end of program	Parent	4-12	T2 -CPP T3-PCIT	NA (items analyzed separately)	[34; 55; 57]
Social Validity: Degree to which parent actively participated in PT	Parent Engagement Scale	Clinician	7	T2-CPP T3-PCIT	.87	[35]

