Parents randomized to PCIT will be scheduled for weekly individual sessions with the target child led by trained PCIT therapists. Each treatment session is 1 hour. Parents randomized to CPP will be randomized to a weekly parent group led by trained CPP therapists. Each CPP session is 2 hours, scheduled on week-day evenings. Target children do not participate in CPP groups; therefore, childcare will be provided at no charge to facilitate parent attendance. Though PCIT and CPP each prescribe approximately 24 hours of treatment exposure, PCIT occurs over a longer period of time (usually 6-8 months versus CPP which occurs over 3 months). This is because (1) PCIT sessions are 1 hour shorter, and (2) PCIT treatments are delayed when parents cancel or do not show up for appointments whereas CPP group sessions continue even if some parents do not attend. All CPP sessions will be audio recorded and a random selection of CPP sessions will be reviewed for fidelity by [name] at Rush University. A random number of PCIT sessions will be videotaped and reviewed for fidelity by a research colleague certified in PCIT who works at the University of Maryland, [name]. A data use agreement will be obtained between [name] and [name] and [name].

- c. Blinding: parents and therapists cannot be blinded to treatment condition. Research assistants trained to code video recorded parent-child free play and clean-up sessions will be blind to treatment condition and hypotheses.
- d. Participants will have full access to routine care at the Family Center. If a PCIT therapist determines at the beginning of the session that the parent is in crisis (e.g., reports severe depression, domestic violence), or the parent requests using the session to discuss a non-child related crisis, they may decide to use that session for crisis intervention. This session will be documented as a non-PT session and accounted for in the analysis of total PT and non-PT treatment exposure. If the CPP therapist determines that a parent in the parent group is in crisis, or a parent requests to discuss a non-child related crisis, that therapist will meet with the parent after the CPP group to discuss scheduling a separate session.
- e. There is no control or placebo group. Participants in both conditions receive an evidence-based parenting program delivered by trained therapists.

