Application Number: NA_00039328

standard deviations. We will use the more conservative two-sided test. Thus, with 300 participants (150/condition) we will have 99% power to detect this difference using a two-sample comparison of means with alpha=0.05.

Hypothesis testing will mainly be conducted using repeated-measures MANOVA. Should the MANOVA be significant, univariate ANOVA will follow to identify the source of those differences. MANOVA was determined to be a more desirable approach than random regression models because MANOVA corrects for multiple tests of hypotheses. All baseline difference analyses and hypothesis testing will be conducted using 2-tailed tests and alpha =.05 (except tests to examine baseline differences between conditions, which will use .01 to correct for the multiple tests of hypotheses).

d. Early stoppage rules. Interventions will be discontinued if (a) more than 50% of parent participants in either condition report dissatisfaction on consumer satisfaction surveys with their assigned intervention or (b) more than 50% of child participants' CBCL scores (in either condition) worsen from baseline by $> .5$ SD. In this event, the research team will immediately convene with the members of the DSM committee to carefully review the protocol, reasons for dissatisfaction, and recommendations for change. A data safety and monitoring committee will meet early in the first year of the study to make additional recommendations for stoppage rules.

8. Risks

- a. Medical risks. Parent-Child Interaction Therapy and the Chicago Parent Program are psychosocial parent training interventions that have shown no evidence of medical risk. The major risks of this study are disclosure of confidential information and discomfort with the personal nature of some of the survey questions. These risks are no greater than what parents would be exposed to in a mental health treatment setting.
- b. Efforts to minimize risk. Efforts have been taken to minimize risk through appropriate training of research and clinical staff and the use of random number subject identifiers. All therapists have licensed and experienced therapists and have completed the appropriate training (PCIT or CPP).

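### The 99% power and the planned MANOVA/ANOVA treat 300 families as independent although CPP is delivered in shared groups; if correlation specific to those groups outweighs any block effect common to both arms, the between-arm tests err more often than 5%

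*Combined protocol and SAP*

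**What the plan says.** **Sizing.** Section 7c bases the sample size on the CBCL. The null is an absolute difference in post-intervention means above 0.5 SD (5 points, so the implied SD is 10). It then states that "with 300 participants (150/condition) we will have 99% power to detect this difference using a two-sample comparison of means with alpha=0.05".

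**Analysis.** Section 7c makes repeated-measures MANOVA the main method, 2-tailed at 0.05. It adds: "Should the MANOVA be significant, univariate ANOVA will follow to identify the source of those differences". Mixed models were considered and set aside: "MANOVA was determined to be a more desirable approach than random regression models because MANOVA corrects for multiple tests of hypotheses".

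**Delivery.** Section 4b: "Parents randomized to CPP will be randomized to a weekly parent group led by trained CPP therapists". By contrast, "Parents randomized to PCIT will be scheduled for weekly individual sessions with the target child led by trained PCIT therapists". Section 3 (Chicago Parent Program) gives the group size: "Typically, 8-12 parents are enrolled in a 12-session CPP group", with two trained leaders per group. Section 5 counts 13 participating clinicians in all and does not split them by arm.

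**Blocks.** Section 4a: "Each block will consist of the next 19 eligible parents (estimated recruitment time=3-4 months"). Section 4b: "parents will be assigned to the appropriate block consisting of the next CPP group or the next available PCIT therapist". Each block therefore feeds both arms.

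The only covariates named for the analysis are additional therapies (Section 4a). No section gives an ICC, a design effect, or a term for group, block or clinician.

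**The concern.** Parents in one CPP group share leaders, discussion and calendar time, so their outcomes may be correlated. PCIT families share no group. If the analysis ignores that correlation, the standard error of the arm difference can be too small.

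Three kinds of conclusion are exposed.

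- **Superiority hypotheses.** Objective 3 predicts that CPP does better on attendance, engagement and satisfaction, which Section 7a lists as primary. Too small a standard error can yield false claims for CPP. Table 1 has the clinician rate engagement, so families with the same leader or therapist may also share a rater.
- **Equivalence read as no significant difference.** Excess rejection then counts falsely against CPP.
- **Equivalence tested against the 0.5 SD null of Section 7c.** The same understatement then declares equivalence too readily, in CPP's favour.

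The reason given for MANOVA is control of multiple testing. If the MANOVA test itself exceeds 5%, that control is lost. The models set aside for that reason are the ones that could carry the clustering.

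**Working it through.** **Inputs.** From the documents: n = 150 per arm, margin 0.5 SD, alpha 0.05 two-sided, CPP groups of 8-12, blocks of 19. Assumed: one CPP group per block, hence 300/19 = 15.8, or about 16 groups, and m = 19/2 = 9.5 per group; CPP-group ICC of 0.02 / 0.05 / 0.10; full follow-up.

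**1. The plan's figure.** With independent families, in SD units, SE = sqrt(2/150) = 0.1155 and 0.5/SE = 4.33. Power = Phi(4.33 - 1.96) = 99.1%. For equivalence with no true difference, two one-sided tests (TOST) at 0.05 per side give 2 x Phi(4.33 - 1.645) - 1 = 99.3%. A 95% CI inside the margin gives 98.2%. The stated 99% reproduces under independence.

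**2. CPP-group correlation only.** DEFF = 1 + (m - 1) x ICC in the CPP arm. True over naive variance of the difference is R = (1 + DEFF)/2. Two-sided size = 2 x (1 - Phi(1.96/sqrt(R))). Naive TOST error at the margin = Phi(-1.645/sqrt(R)).

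| ICC | DEFF | R | Two-sided size | Size, m = 8 to 12 | TOST error at margin |
|---|---|---|---|---|---|
| 0.02 | 1.17 | 1.085 | 6.0% | 5.8-6.3% | 5.7% |
| 0.05 | 1.425 | 1.2125 | 7.5% | 7.1-8.3% | 6.8% |
| 0.10 | 1.85 | 1.425 | 10.1% | 9.2-11.5% | 8.4% |

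**3. Block effect shared by both arms.** Let rb be the variance share of block (both arms) and rg that of the CPP group. Then R = 1 - rb + (m - 1) x rg/2. At a single time point the naive test over-rejects only if rg > 2 x rb/(m - 1), here 0.235 x rb. For a total CPP-group correlation of 0.05, closed-form size is 7.5 / 5.9 / 5.0 / 4.7 / 4.4% when 0 / 50 / 80 / 90 / 100% of it is shared. Break-even is at 4.25/5.25 = 81% shared.

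**4. MANOVA gate, by simulation.**
- Two-group Hotelling test, three outcomes, assumed between-outcome correlation 0.3: 6.6 / 9.1 / 14.0%, against 5.1% at ICC 0.
- Arm-by-time MANOVA, three time points, five outcomes, m = 10, assumed correlation 0.5 over time and 0.3 between outcomes (3,000 runs): 7.1 / 10.0 / 17.8%, against 5.2%. A block effect constant over time drops out of change from baseline: with rb = rg = 0.05 this gate is still 11.3%.

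**5. Power with the correct, known SE.** SE = sqrt((1 + DEFF)/150) = 0.1203 / 0.1271 / 0.1378. TOST power is 98.8 / 97.8 / 95.3%; 95% CI power is 97.2 / 95.1 / 90.5%. With block and CPP-group variances estimated and Satterthwaite df (3,000 simulated trials), TOST gives 97.8 / 95.7 / 92.6% and the 95% CI 93.9 / 90.5 / 83.9%. The further drop is the cost of estimating the model.

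**6. Leaders repeat across groups.** 16 groups x 2 leaders = 32 leader slots, and there are 13 clinicians in all. A t test on the 16 block-level differences (15 df) holds 5% under group and block effects. With leader pairs reused, and leader ICC = group ICC = 0.02 / 0.05 (assumed), its simulated size is about 9 / 13% with three pairs and 7 / 8.5% with six. A group term alone may therefore not be enough.

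**The case against.** **No ICC is given, so the size of any error is unknown.** This stands. All the inflation figures are conditional. But the stated 99% and the nominal 5% also rest on an ICC, namely zero, and the plan does not say so.

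**Blocks feed both arms, so cohort effects cancel.** This stands in part. A reader might infer that any CPP-group correlation beyond the shared part inflates the error. Step 3 shows otherwise: at 80% shared the single-time-point test is at 5.0%, and beyond that it is conservative. Yet leaders and group discussion exist only in CPP, so sharing above 80% is not a safe default. For change from baseline a constant block effect gives little offset.

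**Power stays high.** This stands for clustering confined to CPP. A reader might infer that the trial is underpowered, but the documents do not support that. Much lower figures arise if PCIT therapists also cluster: with 7 therapists and a therapist ICC of 0.05, 95% CI power is 69.7% and naive size 13.8%. Both that therapist count and that ICC are invented for illustration, so these figures stay outside the finding.

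**The gate may not cover the social-validity outcomes.** This stands. Section 7c says only that testing is mainly by MANOVA. Table 1 measures satisfaction and engagement once, at different times by arm, and analyses satisfaction items separately. If a three-outcome gate does apply, a false claim for CPP on one named outcome rises from about 1.0% to 1.2 / 1.7 / 2.8%: small in absolute terms, but the relative excess remains. If no gate applies, the table in step 2 is the relevant one.

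**Conclusion.** The omission is certain: group delivery in one arm, and no allowance for it in either the sizing or the analysis. Its consequence is conditional. If correlation specific to CPP groups or leaders outweighs any shared block effect, nominal 5% tests run at about 6-10% for ICCs of 0.02-0.10, and a multi-outcome gate runs higher. These figures assume one group of about 9.5 per block, no shared block effect and full follow-up.

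On equivalence, a reader might infer that the error only works against CPP. It does not. Against the 0.5 SD null, a naive TOST also accepts a difference at the margin 5.7-8.4% of the time instead of 5%. The plan does not name TOST; that is the natural test of the null it states.

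The main damage is to error rates, with a modest loss of power. It should be fixed before analysis, and it does not put the design in doubt.

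**What to change.** **Main model.** For the main between-arm comparisons, use a partially nested mixed model with:
- randomization block as a factor;
- a random CPP-group effect in the CPP arm only;
- clinician effects in both arms where estimable (leader or leader pair in CPP, therapist in PCIT), otherwise as a prespecified sensitivity analysis;
- repeated measures within family;
- Satterthwaite or Kenward-Roger df.

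Use the same clustering terms for attendance, engagement and satisfaction, in models suited to their scale. Judge equivalence from this model's interval against the 0.5 SD margin. Say that the nominal error rate holds only if the modelled effects cover the real clustering.

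**Multiplicity.** State a rule to replace the MANOVA gate. Holm within each aim is one option; the choice is the sponsor's.

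**Power.** Replace the single 99% with a range and name the test. For example: assuming a CPP-group ICC of 0.02-0.10, no clinician clustering, full follow-up and no true difference, power for the 0.5 SD margin is about 98-93% (TOST, 0.05 per side) or 94-84% (95% CI) with estimated variances. Show clinician clustering and loss to follow-up as separate, explicitly assumed scenarios.

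**Cost.** Group, block and clinician identifiers must be kept in the dataset. Intervals will be slightly wider and the power figure less favourable. With few clinicians, their variances are poorly estimated, so modelling them can be conservative. No new assessments and no extra enrolment.
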